8.1.2 Methods for Evaluation of Measurable Disease

All measurements should be taken and recorded in metric notation using a ruler or calipers. All baseline evaluations should be performed as closely as possible to the beginning of treatment and never more than 4 weeks before the beginning of the treatment.

The same method of assessment and the same technique should be used to characterize each identified and reported lesion at baseline and during follow-up. Imaging-based evaluation is preferred to evaluation by clinical examination unless the lesion(s) being followed cannot be imaged but are assessable by clinical exam.

Clinical lesions Clinical lesions will only be considered measurable when they are superficial (e.g., skin nodules and palpable lymph nodes) and ≥10 mm diameter as assessed using calipers (e.g., skin nodules). In the case of skin lesions, documentation by color photography, including a ruler to estimate the size of the lesion, is recommended.

Chest x-ray: Lesions on chest x-ray are acceptable as measurable lesions when they are clearly defined and surrounded by aerated lung. However, CT is preferable.

Conventional CT and MRI: This guideline has defined measurability of lesions on CT scan based on the assumption that CT slice thickness is 5 mm or less. If CT scans have slice thickness greater than 5 mm, the minimum size for a measurable lesion should be twice the slice thickness. MRI is also acceptable in certain situations (e.g. for body scans), but NOT lung.

Use of MRI remains a complex issue. MRI has excellent contrast, spatial, and temporal resolution; however, there are many image acquisition variables involved in MRI, which greatly impact image quality, lesion conspicuity, and measurement. Furthermore, the availability of MRI is variable globally. As with CT, if an MRI is performed, the technical specifications of the scanning sequences used should be optimized for the evaluation of the type and site of disease. Furthermore, as with CT, the modality used at follow-up should be the same as was used at baseline, and the lesions should be measured/assessed on the same pulse sequence. It is beyond the scope of the RECIST guidelines to prescribe specific MRI pulse sequence parameters for all scanners, body parts, and diseases. Ideally, subsequent image acquisitions should use the same type of scanner and follow the baseline imaging protocol as closely as possible. If possible, body scans should be performed with breath-hold scanning techniques.

PET-CT: At present, the low dose or attenuation correction CT portion of a combined PET-CT is not always of optimal diagnostic CT quality for use with RECIST measurements. PET-CT scans are not always done with oral and IV contrast. In addition, the PET portion of the CT introduces additional data which may bias an investigator if it is not routinely or serially performed. For these reasons, the GOG will not allow PET-CT use for RECIST 1.1 response criteria.

FDG-PET While FDG-PET response assessments need additional study, it is sometimes reasonable to incorporate the use of FDG-PET scanning to complement CT scanning in assessment of progression (particularly possible 'new' disease). New lesions on the basis of FDG-PET imaging can be identified according to the following algorithm:

- a. Negative FDG-PET at baseline, with a positive FDG-PET at follow-up is a sign of PD based on a new lesion.
- b. No FDG-PET at baseline and a positive FDG-PET at follow-up: If the positive FDG-PET at follow-up corresponds to a new site of disease confirmed by CT, this is PD. If the positive FDG-PET at follow-up is not confirmed as a new site of disease on CT, additional follow-up CT scans are needed to determine if there is truly progression occurring at that site (if so, the date of PD will be the date of the initial abnormal FDG-PET scan). If the positive FDG-PET at follow-up corresponds to a preexisting site of disease on CT that is not progressing on the basis of the anatomic images, this is not PD.
- c. FDG-PET may be used to upgrade a response to a CR in a manner similar to a biopsy in cases where a residual radiographic abnormality is thought to represent fibrosis or scarring. The use of FDG-PET in this circumstance should be prospectively described in the protocol and supported by diseasespecific medical literature for the indication. However, it must be acknowledged that both approaches may lead to false positive CR due to limitations of FDG-PET and biopsy resolution/sensitivity.

Note: A 'positive' FDG-PET scan lesion means one which is FDG avid with an uptake greater than twice that of the surrounding tissue on the attenuation corrected image.

Ultrasound: Ultrasound is not useful in assessment of lesion size and should not be used as a method of measurement. Ultrasound examinations cannot be reproduced in their entirety for independent review at a later date and, because they are operator dependent, it cannot be guaranteed that the same technique and measurements will be taken from one assessment to the next. If new lesions are identified by ultrasound in the course of the study, confirmation by CT or MRI is advised. If there is concern about radiation exposure at CT, MRI may be used instead of CT in selected instances.

Endoscopy, Laparoscopy: The utilization of these techniques for objective tumor evaluation is not advised. However, such techniques may be useful to confirm complete pathological response when biopsies are obtained or to determine relapse in trials where recurrence following complete response (CR) or surgical resection is an endpoint.

CA-125 (Ovarian, fallopian tube and primary peritoneal cancer trials): CA-125 cannot be used to assess response or progression in this study. If CA-125 is initially above the upper normal limit, it must normalize for a patient to be considered in complete clinical response. Specific guidelines for CA-125 response (in recurrent ovarian cancer) have been published [JNCI 96:487-488, 2004]. In addition, the Gynecologic Cancer Intergroup has developed CA-125 progression criteria that are to be integrated with objective tumor assessment for use only in first-line trials in ovarian cancer [JNCI 92:1534-1535, 2000].

Cytology, Histology: These techniques can be used to differentiate between partial responses (PR) and complete responses (CR) in rare cases, e.g., residual lesions in tumor types, such as germ cell tumors, where known residual benign tumors can remain.

It is mandatory to obtain cytological confirmation of the neoplastic origin of any effusion that appears or worsens during treatment when measurable disease has met criteria for response or stable disease. This confirmation is necessary to differentiate response or stable disease versus progressive disease, as an effusion may be a side effect of the treatment.

8.1.3 Response Criteria

8.1.3.1 Evaluation of Target Lesions Response Criteria - Evaluation of Target Lesions

Complete Response (CR)	Disappearance of all target lesions. Any pathological lymph nodes (whether target or non-target) must have reduction in short axis to <10 mm
Partial Response (PR)	At least a 30% decrease in the sum of the diameters of target lesions, taking as reference the baseline sum diameters
Progressive Disease (PD)	At least a 20% increase in the sum of the diameters of target lesions, taking as reference the smallest sum on study (this includes the baseline sum if that is the smallest on study). In addition to the relative increase of 20%, the

	sum must also demonstrate an absolute increase of at least 5 mm. (Note: the appearance of one or more new lesions is also considered progressions).
Stable Disease (SD)	Neither sufficient shrinkage to qualify for PR nor sufficient increase to qualify for PD, taking as reference the smallest sum diameters while on study
Clinical Benefit	CR+PR+SD Progression-free survival

8.1.3.2 Evaluation of Non-Target Lesions

Response Criteria - Evaluation of Non-Target Lesions

Complete Response (CR)	Disappearance of all non-target lesions and normalization of tumor marker level. All lymph nodes must be non-pathological in size (<10 mm short axis) Note: If tumor markers are initially above the upper normal limit, they must normalize for a patient to be considered in complete clinical response.
Non-CR/ Non-PD	Persistence of one or more non-target lesion(s) and/or maintenance of tumor marker level above the normal limits
Progressive Disease (PD)	Appearance of one or more new lesions and/or unequivocal progression of existing non-target lesions. Unequivocal progression should not normally trump target lesion status. It must be representative of overall disease status change, not a single lesion increase.
Not evaluable (NE)	When at least one non-target lesion is not evaluated at a particular time point

8.1.3.3 Evaluation of Biomarkers

If serum CA-125 is initially above the upper normal limit, it must normalize for a patient to be considered in complete clinical response.

Progression cannot be based upon biomarkers, such as serum CA- 125, for this study.

8.1.3.4 Evaluation of Best Overall Response

The best overall response is the best response recorded from the start of the treatment until disease progression/recurrence (taking as reference for progressive disease the smallest measurements recorded since the treatment started). The patient's best response assignment will depend on the achievement of both measurement and confirmation criteria.

Evaluation of Overall Response

Target Lesions	Non- Target Lesions	New Lesions	Overall Response	Best Overall Response when Confirmation is Required*
CR	CR	No	CR	>4 wks. Confirmation**
CR	Non- CR/Non- PD	No	PR	> 4 wks. Confirmation**
CR	Not evaluated	No	PR	
PR	Non- CR/Non- PD/not evaluated	No	PR	
SD	Non- CR/Non- PD/not evaluated	No	SD	documented at least once > 4 wks. from baseline**
PD	Any	Yes or No	PD	no prior SD, PR or CR
Any	PD***	Yes or No	PD	
Any	Any	Yes	PD	

^{*} See RECIST 1.1 manuscript for further details on what is evidence of a new lesion.

Note: Patients with a global deterioration of health status requiring discontinuation of treatment without objective evidence of disease progression at that time should be reported as "symptomatic deterioration." Every effort should be made to document the objective progression even after discontinuation of treatment.

^{**} Only for non-randomized trials with response as primary endpoint.

^{***} In exceptional circumstances, unequivocal progression in non-target lesions may be accepted as disease progression.

For Patients with Non-Measurable Disease (i.e., Non-Target Disease)

Non-Target Lesions	New Lesions	Overall Response
CR	No	CR
Non-CR/non-PD	No	Non-CR/non-PD*
Not all evaluated	No	not evaluated
Unequivocal PD	Yes or No	PD
Any	Yes	PD

^{* &#}x27;Non-CR/non-PD' is preferred over 'stable disease' for non-target disease since SD is increasingly used as an endpoint for assessment of efficacy in some trials so to assign this category when no lesions can be measured is not advised

Complete or partial responses may be claimed only if the criteria for each are met at a subsequent time point at least 4 weeks later.

8.1.4 Frequency of Tumor Re-evaluation

In the present study, tumors will be re-evaluated by CT scan of the chest, abdomen, and pelvis every 12 weeks during treatment and at least 4 weeks after the first observation of a complete or partial response. After discontinuation of protocol treatment, patients who have not progressed will still be re-evaluated every 12 weeks.

8.1.5 Date of Progression

Date of progression is defined as the first day when the RECIST (version 1.1) criteria for PD are met. CA 125 (GCIG) progression alone is **not** sufficient for progression to be defined.

8.1.6 Reporting of tumor response

All patients included in the study must be assessed for response to treatment, even if there is a major protocol deviation or if they are ineligible, or not followed/re-evaluated. Each patient will be assigned one of the following categories: complete response, partial response, stable disease, progressive disease, early death from malignant disease, early death from toxicity, early death from other cause or unknown (not assessable, insufficient data).

Early death is defined as any death occurring before the first per protocol time point of tumor reevaluation. The responsible investigator will decide if the cause of death is malignant disease, toxicity, or other cause.

Patients for whom response is not confirmed will be classified as "unknown" unless they meet the criteria for stable disease (or the criteria for partial response in case of an unconfirmed complete response). Patients' response will also be classified as "unknown" if insufficient data were collected to allow evaluation per these criteria. See table above for further detail.

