11.4 Secondary and exploratory analyses

Secondary analyses

The proportion of patients who have clinical benefit will be calculated and an estimate of 90% confidence interval will be provided.

The frequency and maximum severity of acute adverse events will be tabulated graded by CTCAE v5.0.

Kaplan-Meier median estimates and graphs will be used to describe PFS and OS survival functions.

Exploratory analyses

Summary statistics (and graphs where it is appropriate) will be done for exploratory biomarker endpoints.

Appropriate methods will be implemented to explore the associations of biomarkers with the response and clinical benefit, e.g., Spearman's correlation coefficient for interval/ordinal type of

biomarker measurements with response or clinical benefit, chis-squared test for nominal type of biomarker measurements with response or clinical benefit.

The purpose of exploratory objective is to explore and possibly generate hypotheses for future study. Therefore there will be no adjustment for multiple tests.

11.5 Only those patients who are deemed "ineligible" or who receive no therapy will be eliminated from the analysis. All patients who receive any therapy will be evaluated for both treatment efficacy and toxicity. While on occasion, circumstances may prevent the determination of treatment efficacy, such patients will be included in the analysis and labeled as "unknown". This category will be listed and be reflected in the calculation of the response rate.

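### Read literally, 8.1.6 makes a first-scan PR that is followed by PD or by no evaluable scan 'unknown', so she is lost from clinical benefit, while slightly smaller shrinkage with the same course counts as SD.

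*Combined protocol and SAP*

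**What the plan says.** Four parts of the plan act together.

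- **Confirmation (8.1.3.4).** "Complete or partial responses may be claimed only if the criteria for each are met at a subsequent time point at least 4 weeks later".
- **Failure to confirm (8.1.6).** "Patients for whom response is not confirmed will be classified as 'unknown' unless they meet the criteria for stable disease". A parenthesis adds one further route: "or the criteria for partial response in case of an unconfirmed complete response". No matching route from PR to SD is written.
- **Definitions (8.1.3.1).** PR is "At least a 30% decrease in the sum of the diameters of target lesions, taking as reference the baseline sum diameters". SD is "Neither sufficient shrinkage to qualify for PR nor sufficient increase to qualify for PD, taking as reference the smallest sum diameters while on study".
- **Best-response table (8.1.3.4).** SD must be "documented at least once" at 4 weeks or more from baseline. PD as best response carries the condition "no prior SD, PR or CR".

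Clinical benefit is CR, PR or SD (2.4.2, 11.1.2). Section 11.4 states: "The proportion of patients who have clinical benefit will be calculated and an estimate of 90% confidence interval will be provided". Section 11.5 keeps patients labelled unknown in the analysis. For the primary endpoint, 11.3 groups SD, PD and unknown together as non-response.

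**The concern.** The unknown category in 8.1.6 is meant for patients who cannot be assessed or whose data are insufficient. A patient with PR at week 12 and PD at week 16 has been measured twice, and the first measurement showed a shrinking tumor. The written rules still leave her nowhere else to go: PR is not confirmed, no scan is in the SD range, and PD is barred as best response by the earlier PR. Had her tumor shrunk slightly less, the same course would have made her SD and a clinical benefit success. For these patients the rule ranks deeper shrinkage below shallower shrinkage.

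Two analyses are exposed: the clinical benefit rate, which is a secondary endpoint, and the exploratory associations of biomarkers and genomic signatures with clinical benefit, where such a patient would sit in the no-benefit group.

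**Working it through.** **1. The plan's own figures.** The documents give no figure for clinical benefit or for unconfirmed responses. The only related figures are the operating characteristics of the primary design in 11.3. An exact two-stage binomial calculation, averaged with equal weight over the 8 × 8 = 64 combinations of stage 1 size (19-26) and cumulative size (44-51) with the stated cut-offs, gives:

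| Quantity | Stated | Recomputed |
|---|---|---|
| Early termination at 10% | 64% | 63.6% |
| Type I error at 10% | 10% | 9.9% |
| Power at 25% | 90% | 90.0% |

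These reproduce. They depend only on response versus non-response, so moving a patient between unknown and SD leaves them unchanged.

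**2. Rule check.** I applied 8.1.3.1, 8.1.3.4 and 8.1.6 literally to example courses with a baseline sum of 100. PR is a sum of 70 or less. PD is an increase of at least 20% and at least 5 mm over the smallest sum. Anything between is SD. Where PD follows, the later sum was 95 (65 for the 60% case).

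| Course | Scan by scan | Best response | Clinical benefit |
|---|---|---|---|
| −32% week 12, PD week 16 | PR, PD | unknown | no |
| −60% week 12, PD week 16 | PR, PD | unknown | no |
| −29% week 12, then PD | SD, PD | SD | yes |
| −32% week 12, no further evaluable scan | PR | unknown | no |
| −29% week 12, no further evaluable scan | SD | SD | yes |
| −32% week 12, −25% week 16 | PR, SD | SD | yes |
| −15% week 12, −32% week 24, then PD or no scan | SD, PR | SD | yes |
| −32% week 12, −33% week 16 | PR, PR | PR | yes |

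The inversion appears only when the unconfirmed PR is the sole evaluable assessment before PD or before scans stop. The exception in 8.1.6 applies to the patient, not to the scan, so any SD-range scan at least 4 weeks from baseline rescues her.

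**3. Can this course occur?** Scans are every 12 weeks, with a further one at least 4 weeks after a first response (8.1, 8.1.4). PR at week 12 and PD at week 16 fits that schedule. A patient who stops treatment and starts another anticancer therapy after week 12 leaves tumor assessment (6.4) and may never have the confirming scan.

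**4. Size per patient.** With unknowns kept in the denominator (11.5), each affected patient costs 1/N: 1/48 = 2.1 points at the target, 1/44 = 2.3 and 1/51 = 2.0 at the ends of the permitted range.

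**5. Illustration.** Section 1.3 reports 9% response plus 62% SD with earlier hormonal therapy. Assume that 71% applies here: 0.71 × 48 = 34.1, so 34 patients with benefit if an unconfirmed PR steps down to SD. The number affected is an assumption. Intervals are exact (Clopper-Pearson) 90%.

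| Affected | Rate under literal rule | 90% interval |
|---|---|---|
| 0 | 34/48 = 70.8% | 58.2-81.4% |
| 1 | 33/48 = 68.8% | 56.0-79.6% |
| 2 | 32/48 = 66.7% | 53.9-77.8% |
| 3 | 31/48 = 64.6% | 51.7-76.0% |

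Four patients would be 4/48 = 8.3 points. The half-width at 34/48 is (81.4 − 58.2)/2 = 11.6 points.

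**The case against.** The best defence is that a step-down to SD was intended. Section 8.1.3.4 makes best response depend on both measurement and confirmation, 8.1.6 refers back to the table, the table's SD entry in the confirmation column is a timing condition, and the CR-to-PR parenthesis points the same way. This is plausible, but it is written nowhere for PR. The CR case also differs in kind: PR is bounded on one side, so a CR-sized decrease passes its threshold, whereas SD is bounded on both sides and excludes a PR-sized decrease. Two statisticians could code the same patient differently.

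The second defence is that the effect is narrow, and that stands. A reader might infer that every unconfirmed PR is lost from clinical benefit. The documents do not support that, since one SD-range scan before or after is enough. The added scan after a first response may itself confirm the PR or fall in the SD range, and either keeps the patient in clinical benefit.

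The third defence is that little depends on the endpoint. Clinical benefit is described with an interval and has no test or decision rule, the biomarker work is hypothesis-generating, and 11.5 requires the unknowns to be listed, so the affected patients could be found and re-tabulated. That also stands. It limits the weight of the point but does not make the written rule correct.

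**Conclusion.** The point holds in a limited form. On the literal text, a PR at the first evaluable scan followed directly by PD or by no evaluable scan is unknown and lost from clinical benefit, while shrinkage just under 30% with the same course counts. The bias is always downward, at 2.1 points per affected patient (2.0-2.3 over the permitted final sizes). This assumes the trial completes stage 2 and that 11.5 sets the denominator for clinical benefit.

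Three stronger conclusions are not supported:

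- **A stated total bias.** The documents give no rate of non-confirmation, still less of non-confirmation with no SD-range scan at any visit. The 2 to 8 points for 1 to 4 patients is an illustration only.
- **A reversed biomarker association.** Placing shrinking tumors in the no-benefit group can weaken an association with benefit. Nothing in the documents shows that it would reverse one.
- **An effect on the primary result.** SD and unknown are both non-response, so the response count and the stage 1 and final decisions are unchanged.

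**What to change.** Keep the present sentence in 8.1.6, including its step-down from unconfirmed CR to PR, and add after it:

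*An unconfirmed PR (or an unconfirmed CR that does not qualify as PR) seen at or beyond the minimum interval for SD (at least 4 weeks from baseline) is classified as stable disease for best overall response and does not count as an objective response.*

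Align the best-response table in 8.1.3.4 with this.

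The CR-to-PR step-down must stay. A blanket rule sending every unconfirmed CR or PR to SD would turn a CR at week 12 with a PR-range scan at week 16, which the present text allows to be PR, into a non-responder. With cut-offs of 2 or 3 responses at stage 1 and 6 or 7 at the end, one such patient could change the decision.

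The cost is one sentence and a table edit before analysis. No extra scans or data are needed, and the primary response count does not change.

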8.1.7 Duration of Response

Duration of overall response: The duration of overall response is measured from the time measurement criteria are met for CR or PR (whichever is first recorded) until the first date that recurrent or progressive disease is objectively documented (taking as reference for progressive disease the smallest measurements recorded since the treatment started).

The duration of overall CR is measured from the time measurement criteria are first met for CR until the first date that progressive disease is objectively documented.

Duration of stable disease: Stable disease is measured from the start of the treatment until the criteria for progression are met, taking as reference the smallest measurements recorded since the treatment started, including the baseline measurements.

8.1.8 Progression-free survival: Progression-free survival (PFS) is defined as the duration of time from study entry to time of progression or death or the date of last contact, whichever occurs first.

